2.3 Disposition of patients

The number of patients eligible for inclusion in the study, treated and completing the study will be summarized and presented graphically in a CONSORT style diagram using the All Enrolled Set.

For all patients in the FAS not completing the study, the reason for early termination will be summarized and included in the diagram.

2.4 Statistical methods

2.4.1 Reporting conventions

All summary tables will be presented overall and by subpopulation (prospective/retrospective). In addition, three distinct cohorts will be identified depending on the type of surgery performed: free flaps, replantation, or lymphatic surgery. Note, as described in figure 1, a patient may have more than one type of procedure and/or an operation may include more than one of a type of procedure (e.g. two flap operations). On all tables the unit of analysis will be clearly indicated. The number of patients involved as well as the number of units with non-missing data will be clearly indicated in summary tables. In addition, the number of units with missing data will also be included to aid data interpretation.

Sponsor: MMI Product: Symani system for microsurgical anastomosis Study: PRIMO	
Statistical Analysis Plan Final 22 November 2024	

Continuous variables (such as age) will be summarized using descriptive statistics (n (the number of observations), mean, median, standard deviation (SD), minimum and maximum). Categorical variables (such as gender) will be summarized using frequency tables (frequencies and percentages). All mean and median values will be formatted to one more decimal place than the measured value. Standard deviation values will be formatted to two more decimal places than the measured value. Minimum and maximum values will be presented to the same number of decimal places as the measured value. All percentages will be rounded to one decimal. The number and percentage of responses will be presented in the form XX (XX.X%), where the percentage is in parentheses.

All patient data listings will be sorted by patient ID number, sub-population (prospective/retrospective) and time point (if applicable).

All analysis and summary tables will have the analysis population sample size in the column headers in the form of N=XXX.

2.4.2 Demographics and baseline characteristics

Demographics (age, sex, race) will be presented using descriptive statistics. Height, weight, and BMI will be presented using descriptive statistics. All data will be listed.

Frequency tables for risk factors collected as part of the screening procedures and for lymphedema stage (LVA operations only) will be produced.

Medical history data will be listed.

Physical examination information will be listed.

2.4.3 Operation information

Information recorded for use of medications will be presented with frequency tables.

The time in OR and duration of procedure will be presented with descriptive statistics.

Details of donor site and recipient site will be presented using frequency tables.

All data will be listed.

The number of procedures performed during the index operation will be presented using frequency tables. In addition, the number of each type of procedure (ie flaps, replantations, lymphatic) in the index operation will be presented using frequency tables.

The number of anastomoses in the index procedure will be determined and presented using frequency tables.

Information collected for each anastomosis will be presented using appropriate summary tables (descriptive statistics or frequency tables), where n is the total number of anastomoses, which will be \geq the number of patients.

Sponsor: MMI Product: Symani system for microsurgical anastomosis Study: PRIMO	
Statistical Analysis Plan Final 22 November 2024	

2.4.4 Analysis of effectiveness variables

Note on analysis models/approach.

For all binary outcomes a simple frequency table presenting number and percentage (with confidence limits) will be produced, where the denominator will be the unit of analysis (patient, surgery type, procedure or anastomosis). The confidence limits produced will be biased as they assume independent observations whilst repeat assessments on the same patient (ie > 1 anastomosis/procedure, >1 procedure/patient) are not independent.

To explore the extent of dependence in the data, a table will be produced to describe the hierarchy in the data (as per fig 1), namely:

- Number of patients.
- Number of surgery types (flap, replantation, lymphatic)/patient (i.e. 1, 2 or 3 different types of surgery).
- Within surgery type, number of procedures/patient (i.e. number of flaps, number of replantations, number of lymphatic procedures).
- Within each procedure, number of anastomoses/procedure and also number of anastomoses/patient.

In the simplest scenario there will be one surgery type/patient, one procedure/patient and for that procedure only one anastomosis (so at all levels there is one/patient).

The most complex structure is each patient has all three surgery types, with multiple procedures of each type and for each procedure there are multiple anastomoses.

In addition to these levels of dependence due to repeated observations on the same patient, the results are expected to be influenced by surgeon. Accordingly, for the main analysis of all effectiveness endpoints, a mixed model will be employed where surgeon will be included as a random term.

All models will be fitted separately for each surgery type (free flaps, replantations, lymphatic).

In all models fixed effects for subpopulation (prospective/retrospective) and recipient site/location will also be included to facilitate estimation by subpopulation and recipient site/location. For analysis of replantations a further fixed effect will be included for procedure type (free or nerve).

The analysis models described below (where the unit of analysis is not the patient), allows for the most complex structure of data dependence/repeated measures; namely recipient site/location will be included as a fixed effect (as noted above), but procedure number (within type) and anastomosis number (within procedure for analyses where the unit of analysis is at the anastomosis level) will be included as random terms as required to acknowledge the repeated measures in the data. A decision will be made on production of the initial summary table on the level of complexity required for each analysis. Note, for all endpoints (unless otherwise specified) separate models will be fitted for each surgery type and all models for replantations will include the additional fixed effect of procedure type (free or nerve).

Sponsor: MMI Product: Symani system for microsurgical anastomosis Study: PRIMO	
Statistical Analysis Plan Final 22 November 2024	

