PRIMO	PRIMO Study Protocol	CDC-00031 Rev. 03 Page: 1/1
--------------	---------------------------------------	-----------------------------------

PRIMO Study Protocol

Protocol Number: CDC-00031

NCT04843436

SPONSOR DOCUMENT APPROVALS

Role	Name / Function
Issuer	[name] Clinical Operations Project Manager, Clinical Affairs
Reviewer & Approver	[name] Associate Director, Clinical Affairs
Reviewer & Approver	[name] VP, Regulatory Affairs

Reference ARENA PLM for document approvals and approval date.

Revision History		
REV	DATE	DESCRIPTION
00	10MAR2020	N/A, first issue
1.0	17NOV2020	Modified from Observational to Post-market clinical study
2.0	20OCT2021	Updates in accordance to EU MDR 2017/745 and ISO 14155:2020; Follow-up visit for free flap, replantation and other procedures extended to 30±7 days
3.0	11AUG2022	Addition of protocol description

**RASM
POST MARKET CLINICAL FOLLOW-UP
STUDY
Synopsis**

CDC-00031
Rev. 03
Page: 1/4

**PRIMO: Post-Market, Non-Randomized, Multicentre PMCF Study To Monitor
The Safety And Performance Of Symani System In Microsurgical
Reconstructive Procedures In A Real Life Setting**

Protocol Synopsis

Study Objectives	The objective of this PMCF study is to monitor the safety, usability, performance and long-term efficacy of the Symani System.
Study Device	Symani System for Microsurgery (Symani)
Indication for Use	
The Symani System is a CE-marked device and it is intended for soft tissue manipulation to perform microsurgery techniques such as anastomosis, suturing, and ligation on small anatomical structures, including blood vessels and lymphatic ducts, in open surgery procedures.
 
The Symani System teleoperated-instruments are indicated for use during microsurgical procedures when use of a motion scaling function is deemed appropriate by the surgeon.
 
The Symani System is not intended for use on the heart, central circulatory system, central nervous system, or the eye. The system is indicated for adult and pediatric use, even if in the present study, only adult population will be enrolled. It is intended to be used by trained physicians in an appropriate operating environment in accordance with the Instructions for Use.

Study Design	
A prospective, single-arm, open-label, clinical study designed to evaluate the Symani System safety and effectiveness for microsurgical anastomosis.
 
The study will be conducted in at least 3 centers in Europe.

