1.7 Determination of sample size

The planned minimum sample size is 402 patients. The primary endpoint for the study is technical performance, assessed as a binary outcome procedural success Yes/No. Procedural success will be assessed at the anastomosis level; each patient may have > 1 anastomosis. Based on data published in the medical literature (see RASM Literature Review Report [5]), the traditional failure and complication rate for vascular anastomoses is 15%, implying a success rate of 85%. The study will have 85% power to conclude that a success rate using Symani of 89% (or higher) is better than the literature value if a minimum of 402 anastomoses operations are performed. The percentage success will be estimated and exact 95% confidence limits calculated. If the lower 95% confidence limit exceeds 85% then the conclusion can be reached that Symani is superior to manual surgical methods. As each patient may have more than one anastomosis operation, the number of anastomoses will be ≥ 402 from 402 patients, providing increased power. As the number of anastomoses/patient is unknown at the time of study design, the conservative approach of recruiting 402 patients has been followed.

The number of patients missing a response for the primary endpoint will be monitored and additional patients may be recruited if deemed necessary.

There will be no predetermined limit to the number of sites that can participate in the study. Patients enrolled under the retrospective data collection protocol addendum will contribute to the planned sample size for the entire study (prospective plus retrospective).

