2.4.4.1 Analysis of primary effectiveness variable – procedure robotic success

As per section 2.1.3.1 each anastomosis for each patient in the FAS will be assigned to ‘Yes’ or ‘No’ for procedure robotic success. This represents a binary outcome. The analysis of this variable is at the anastomosis level.

For each surgery type (replantation, free flap or lymphatic surgery) stratified frequency tables will be presented stratified by subpopulation (prospective/retrospective) and recipient site/location. The denominator is the number of anastomoses. The proportion of anastomoses classified as a robotic success by stratum and overall for each surgery type will be presented with 95% confidence limits. Results will also be presented on a forest plot.

For replantations a further stratifying variable will be included, namely procedure type (free/nerve).

For each surgery type, a generalized linear mixed model (GLMM) will be used to estimate the percentage of anastomoses classified as robotic success. In SAS, PROC GLIMMIX will be utilized to analyze the data. Subpopulation (prospective/retrospective), recipient site/location and surgeon experience will be included as fixed effects, and surgeon as a random effect. Procedure number (within a surgery type) and anastomosis number (within a procedure) will be included as random terms to acknowledge the dependence in the data (see note above). From the model the adjusted rate of robotic success will be obtained, with 95% confidence limits, for each type of surgery overall and by recipient site/location, by surgeon experience and by subpopulation. (Model 1).

Fixed effects

For free flaps, recipient site will be head and neck, extremities, breast or other.

For lymphatic surgery location will be heads and neck, upper limbs or lower limbs

For replantations there will also be a factor for procedure type (free or nerve), as well as recipient site (as for free flaps) (Model 1a) and results also obtained by procedure type (free/nerve).

For all types of surgery, surgeon experience is classified as microsurgeon, fellow, resident.

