2.5 Statistical/ Analytical Issues

2.5.1 Adjustments for covariates

Surgery type (flap, replantation, lymphatic) and subpopulation (prospective/retrospective) are included as fixed factors where applicable in the primary and secondary efficacy modelling. Results by these factors are included in tables and forest plots produced for the study.

Surgeon is included as a random effects term in each of the models.

Procedure number/anastomosis number (within patient) are included in models where relevant to acknowledge dependence in the data.

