Appendix 1. Summary of endpoints, unit of analysis and analysis method

Endpoint	Level	analysis
Robotic success	Anastomosis	GLMM. Bernoulli form by stype Fixed: recipient site/location, subpop For replantations also include procedure type (free or nerve) Random surgeon, procedure number anastomosis number, subject=patient. Model 1/1a.
Robotic usability	Patient	GLMM Binomial form as nsuccess/npats by stype Fixed: recipient site/location. For replantations also include procedure type (free or nerve) Random surgeon. Model 2./2a
Anastomosis time	Anastomosis	GLMM normal by stype Fixed: recipient site/location, subpop For replantations also include procedure type (free or nerve) Random surgeon, procedure number anastomosis number, subject=patient. Model 3/3a
Intra-operative redo	Anastomosis	Model 1/1a
Post-op redo	Procedure	GLMM Bernoulli form by stype Fixed: recipient site/location, subpop For replantations also include procedure type (free or nerve),

Sponsor: MMI Product: Symani system for microsurgical anastomosis Study: PRIMO	
Statistical Analysis Plan Final 22 November 2024	

		Random surgeon, procedure number subject=patient. Model 4/4a
Complications	Patient	Safety endpoint. Summaries of AEs
Warm ischemia time		
Flap loss/failure	Procedure	Model 4/4a
Limb volume reduction	Procedure	GLMM normal Fixed timepoint. Cov baseline vol. Random surgeon, procedure number subject=patient. Model 5.
Free flap viability at 30 days	Procedure	Model 4/4a
Intra-operative anastomosis patency	Anastomosis	Model 1/1a
Rate of intra-operative approach change	Anastomosis	Model 1/1a
Freedom from device related SAE at discharge	Patient	Simple frequency and exact CL
Freedom from device related AE at discharge	Patient	Simple frequency and exact CL
All cause re-admission rate	Patient	KM. Use PL to get rate within 30 days
All cause re-op rate	Patient	KM. Use PL to get rate within 30 days
All cause mortality rate	Patient	KM. Use PL to get rate within 30 days
Length of hospital stay	Patient	Descriptive stats

PRIMO Statistical Analysis Plan

Final Audit Report

2024-12-13

Created:	2024-12-11
By:	[name] ([contact])
Status:	Signed
Transaction ID:	CBJCHBCAABAAHjF3YtYJkG7xb1_tZngZ89-skKZM8HiF

"PRIMO Statistical Analysis Plan" History

-  Document created by [name] ([contact])
2024-12-11 - 4:57:01 PM GMT
-  Document emailed to [name] ([contact]) for signature
2024-12-11 - 4:57:09 PM GMT
-  Document emailed to [name] ([contact]) for signature

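### Appendix 1 lists surgeon under subject=patient, which coded literally treats one surgeon's patients as independent; and no model includes centre, so limits may be too narrow where centres have several surgeons

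*SAP*

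**What the plan says.** The study is multicentre. The protocol synopsis says "The study will be conducted in at least 3 centers in Europe", and SAP 1.7 adds "There will be no predetermined limit to the number of sites that can participate in the study".

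The hierarchy in SAP section 2 runs from patient to surgery type, procedure and anastomosis. Section 2.4.4 then adds surgeon: "In addition to these levels of dependence due to repeated observations on the same patient, the results are expected to be influenced by surgeon". It concludes that "for the main analysis of all effectiveness endpoints, a mixed model will be employed where surgeon will be included as a random term". For the primary endpoint, 2.4.4.1 specifies "Subpopulation (prospective/retrospective), recipient site/location and surgeon experience will be included as fixed effects, and surgeon as a random effect", with procedure number and anastomosis number as further random terms. Section 2.5.1 repeats: "Surgeon is included as a random effects term in each of the models". Section 2.5.6 describes a diagonal covariance structure with equal variances over the levels of the surgeon identifier.

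Appendix 1 gives the primary model's random part as "Random surgeon, procedure number anastomosis number, subject=patient. Model 1/1a". Model 3 (anastomosis time), Model 4 (post-operative redo, flap loss, 30-day viability) and the limb-volume model (Model 6 in 2.4.4.2.8, Model 5 in Appendix 1) follow the same pattern. Model 2 (usability) lists surgeon alone. The Model 3 paragraph in 2.4.4.2.2 names no surgeon term.

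No model contains centre. Where the models refer to site, they mean recipient site. No analysis by centre is planned.

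**The concern.** Two levels of clustering are at issue.

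**Surgeon.** In SAS, the SUBJECT= option nests every effect in its RANDOM statement within the subject. A single statement with surgeon, procedure number and anastomosis number under subject=patient therefore fits surgeon-within-patient. If each patient has one surgeon, that is only a patient intercept, and nothing links two patients of the same surgeon. The dependence that 2.4.4 says it expects would be absent from the fitted model. For Model 3 the endpoint text gives a programmer no surgeon term to set against the appendix line.

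**Centre.** Surgeons at one centre may resemble each other, for example through case selection. The SAP states "For all types of surgery, surgeon experience is classified as microsurgeon, fellow, resident", which makes several operators per centre plausible but does not establish it. A surgeon term without centre treats such colleagues as independent.

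These models are the main analysis of the effectiveness endpoints, so the stake is the width of their 95% limits.

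**Working it through.** The documents give no surgeon or centre variance and no number of surgeons, so there is no plan figure to reproduce. The inputs below are assumptions, shown over a range. All calculations are on a linear scale with balanced data; the primary model is a binary GLMM fitted by surgery type, so the sizes are indicative.

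**1. The texts side by side**

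| Place | Surgeon term |
|---|---|
| 2.4.4, 2.4.4.1, 2.5.1 | random effect, not tied to patient |
| 2.4.4.2.4, 2.4.4.2.8 | random; only procedure number is placed within patient |
| 2.4.4.2.2 (Model 3) | not named |
| 2.5.6 | variances over levels of the surgeon identifier |
| Appendix 1, Model 2 | surgeon alone |
| Appendix 1, Models 1, 3, 4, limb volume | on one line with subject=patient |

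The main text describes an effect shared by a surgeon's patients. The last row, read as code, does not.

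**2. Surgeon nested in patient**

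Assume K = 10 surgeons, P = 15 patients each, 2 anastomoses per patient, patient share of variance 0.15 and surgeon share r. Per patient mean, v = 0.15 + (1 − r − 0.15)/2.

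- True variance of the overall mean: r/K + v/(KP).
- Variance the nested model reports: (r + v)/(KP).
- Coverage: 2Φ(1.96 × √(reported/true)) − 1.

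For r = 0.05: v = 0.55; true = 0.005 + 0.55/150 = 0.00867; reported = 0.60/150 = 0.00400; ratio of SEs 0.68; coverage 82%.

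For r = 0.20: v = 0.475; true = 0.020 + 0.475/150 = 0.02317; reported = 0.675/150 = 0.00450; ratio of SEs 0.44; coverage 61%.

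**3. Surgeon shared across patients, centre omitted**

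Assume C centres, S surgeons per centre, 10 patients per surgeon, 2 anastomoses per patient, patient share 0.15, centre share c and surgeon share r.

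- Variance of a surgeon mean within a centre: w = r + 0.15/10 + (1 − c − r − 0.15)/20.
- True variance of the overall mean: c/C + w/(CS).
- Expected surgeon-only variance: [w + c(CS − S)/(CS − 1)]/(CS).

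With S = 1 the two variances are identical, so omitting centre costs nothing. For C = 6, S = 3, c = r = 0.05: w = 0.1025; true = 0.00833 + 0.00569 = 0.01403; surgeon-only = (0.1025 + 0.0441)/18 = 0.00815; the true SE is 1.31 times the reported one.

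Coverage of nominal 95% limits, simulated for 6 centres as a t interval from surgeon means:

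| Centre share / surgeon share | 2 surgeons | 3 surgeons | 4 surgeons |
|---|---|---|---|
| 1% / 5% | 94% | 93% | 92% |
| 5% / 5% | 91% | 87% | 83% |
| 10% / 10% | 90% | 85% | 80% |

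Results with 3 and 10 centres are within about 1 point of these. Intervals from centre means cover about 95%.

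**4. In percentage points**

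Take 402 single-anastomosis patients pooled over surgery types, a success rate of 89% (the rate assumed in 1.7; variance 0.89 × 0.11 = 0.0979), 3 centres with 3 surgeons each, and c = r = 0.02. The half-width is 1.96 × √(0.0979 × V).

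- Centre and surgeon: V = 0.02/3 + 0.02/9 + 0.96/402 = 0.01128; half-width 6.5 points.
- Surgeon only: V = (0.02 + 0.02 × 6/8)/9 + 0.96/402 = 0.00628; 4.9 points, coverage about 86%.
- Surgeon nested in patient: V = 1/402 = 0.00249; 3.1 points, coverage about 64%.

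**5. Price of modelling centre with few centres**

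With 3 centres and 2 surgeons each, the t multiplier rises from 2.571 (5 df) to 4.303 (2 df). At centre and surgeon shares of 5% or 10% each and 2 to 4 surgeons per centre, the centre-based interval is on average about 1.9 to 2.8 times as wide as the surgeon-only one.

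**The case against.** *Appendix 1 is a summary table, not code.* This stands. The subject=patient label may be meant only for procedure and anastomosis number, and the main text favours a shared surgeon effect. A reader might infer a proven nesting error; the documents show only a specification that contradicts the main text if followed literally. The contradiction still needs resolving, because it covers most of the models.

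*The surgeon term already handles centre.* This stands in part. A reader might infer that correlation within centres is ignored and that the limits are certainly too narrow. The documents do not support that: a shared surgeon effect absorbs all the centre variance with one surgeon per centre and part of it otherwise, and neither surgeons per centre nor between-centre variation is documented. Subpopulation and recipient site or location are fixed effects by the general rule, and Model 1 adds surgeon experience; these may explain some centre differences. At a 1% centre share the loss is only 1 to 3 points of coverage.

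*The benchmark conclusions are untouched.* This largely stands. The decision rule in 1.7 uses exact limits, which no model term alters; the adverse-event comparison is descriptive with exact limits; and the re-operation rate comes from Kaplan-Meier. Only 30-day flap survival joins a mixed model to a literature figure, and there only as a check of consistency.

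*A random centre effect is poorly estimated with 3 centres.* This stands, and is why centre is better placed in a sensitivity analysis.

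**Conclusion.** The point holds in two parts of different strength.

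The Appendix 1 line conflicts with 2.4.4, 2.5.1 and 2.5.6. If it is run as one RANDOM statement, the model-based limits are too narrow, with coverage of about 82% to 61% for surgeon shares of 0.05 to 0.20 under the layout in step 2. If the main text is followed instead, this loss does not arise.

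The absence of centre is certain; its effect is conditional. It needs several surgeons at some centres and real differences between centres. Given both, coverage of about 94% to 80% is plausible over the assumed range. With one surgeon per centre, or no centre variance, there is no loss.

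Both parts concern the model-based limits for the effectiveness endpoints, not the exact limits in 1.7.

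**What to change.** 1. In Appendix 1, for Models 1, 3, 4 and limb volume, give surgeon its own random statement (subject=surgeon, shared across that surgeon's patients). Keep subject=patient only for the procedure and anastomosis terms.
2. Name surgeon as a random effect in the Model 3 text (2.4.4.2.2).
3. Add a prespecified sensitivity analysis with centre: surgeon nested in centre, or fixed centre effects if few centres contribute. Report its limits beside the planned ones.

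Items 1 and 2 are wording changes and bring the appendix into line with the main text. Item 3 costs one further fit per model and needs centre to be identified in the analysis data. Its downside is wider limits, markedly so with only 3 centres, and an imprecise centre variance. If that variance is estimated as zero, the random-centre version reduces to the planned model.
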